#### 5.4.3 Definition of primary outcomes

#### Anemia

Confirmed cases of anemia (clinically relevant) is defined as:

- 1. Confirmed by a repeated reliable laboratory test (e.g. hemoglobin, packed cell volume), plus pertinent therapy (blood or iron transfusion, iron tablets) or
- 2. No reliable laboratory data available, but clinical diagnosis stated by a physician, followed by pertinent therapy (see above) and
- 3. No obvious explanation (such as gastrointestinal bleeding, trauma, major surgery) or no explanation other than endometriosis-related bleeding.

#### **Depression**

Confirmed cases of clinically relevant depression or worsening of existing depression is defined as:

- 1. Diagnosis is confirmed by a physician specialized in psychiatry using validated instruments (e.g. HAM-D, BECK depression inventory)
- 2. Confirmed suicide or attempted suicide in a participant with a past history of depression
- 3. Clinical diagnosis confirmed by a physician specialized in psychiatry without the use of validated instruments (see above)
- 4. Confirmed (attempted) suicide without a previous psychiatric diagnosis

#### Treatment Failure

Treatment failure is defined as:

- 1. Medication ineffective given as a reason for stopping or switching treatment
- 2. Side effects of medication given as a reason for stopping or switching treatment

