There are both pharmacological and clinical indications that suggest that DNG may be superior to other endometriosis medications as a long-term treatment for endometriosis. That is, a statistical comparison of DNG vs. other endometriosis medications may show a difference in 'treatment failure', with DNG users continuing on treatment for longer periods of time. 'Treatment failure' is defined as cessation of treatment caused by lack of efficacy, loss of efficacy or an adverse drug reaction and does not include women who stop treatment after pre-defined treatment periods (eg. after six months for GnRH agonists). *In addition, combined treatment with GnRH, an estrogen and/or a progestogen (add-back therapy) will be considered as a single treatment regimen. In cases where add-back therapy is used the predefined endpoint is the cessation of the add-back therapy.⁸ A superiority design to investigate 'treatment failure' for DNG has been chosen. The analysis will be based on a 5% point difference (difference of 0.05) of DNG vs. other endometriosis medications.*

Safety monitoring during study conduct will be based primarily on the ITT analysis of crude data. The final analyses will include both an "as treated" (AT) and an intention-to-treat (ITT) analysis using Cox regression models. The safety conclusions of the

⁸ The two sentences in italics were was added on request of the MEB (revised study protocol of February 28, 2011)

study, however, will be based on the AT analyses because the ITT approach potentially dilutes differences between treatments.

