There are both pharmacological and clinical indications that suggest that DNG may be superior to other endometriosis medications as a long-term treatment for endometriosis. That is, a statistical comparison of DNG vs. other endometriosis medications may show a difference in 'treatment failure', with DNG users continuing on treatment for longer periods of time. 'Treatment failure' is defined as cessation of treatment caused by lack of efficacy, loss of efficacy or an adverse drug reaction and does not include women who stop treatment after pre-defined treatment periods (e.g. after six months for GnRH agonists). In addition, combined treatment with GnRH, an estrogen and/or a progestogen (add-back therapy) will be considered as a single treatment regimen. In cases where add-back therapy is used the predefined end-point is the cessation of the add-back therapy. A superiority design to investigate 'treatment failure' for DNG has been chosen. The analysis will be based on a 5%-point difference (difference of 0.05) of DNG vs. other endometriosis medications.  $OR_{TreatmentFailure}$  is defined as the odds ratio for 'treatment failure' for DNG vs. OAED.

 $H_0: OR_{TreatmentFailure} \ge 1$ 

 $H_A: OR_{Treatmentfailure} < 1$ 

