#### 5.4.4 Definition of secondary outcomes

#### Treatment pattern

Treatment pattern is defined as:

- 1. Treatment discontinuation not related to treatment failure (treatment duration over, trying to become pregnant, other reasons)
- 2. Cohort status/switch of women during follow-up, considering the first treatment switch after baseline

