#### Section C-1.3 Incidence proportions of treatment discontinuation due to treatment failure

Table C-1.3.1 Incidence proportions of treatment discontinuation due to treatment failure, AT population, Complete cohort

	DNG		OAED			NAED		Allocation unknown	Total
		GnRH-a	Danazol	All OAED	СНС	Other progestin	All NAED		
Number of treatment starts	xx	xx	xx	xx	xx	xx	xx	xx	xx
Treatment failure	xx	xx	xx	xx	xx	xx	xx	xx	xx
IP* (95% CI) Thereof**	xx.x (xx.x–x.x)	xx.x (xx.x–x.x)	xx.x (xx.x-x.x)	xx.x (xx.x-x.x)	xx.x (xx.x–x.x)	xx.x (xx.x-x.x)	xx.x (xx.x–x.x)	xx.x (xx.x–x.x)	xx.x (xx.x–x.x)
Medication ineffective	xx xx.x (xx.x–x.x)			xx xx.x (xx.x–x.x)	xx xx.x (xx.x-x.x)		xx xx.x (xx.x–x.x)		
Side effects  Thereof***	xx xx.x (xx.x-x.x)				xx xx.x (xx.x–x.x)			xx xx.x (xx.x-x.x)	
Depression / Depressive mood	xx xx.x (xx.x-x.x)			xx xx.x (xx.x–x.x)	xx xx.x (xx.x–x.x)			xx xx.x (xx.x–x.x)	
<category>></category>	xx xx.x (xx.x–x.x)			xx xx.x (xx.x-x.x)	xx xx.x (xx.x–x.x)			xx xx.x (xx.x–x.x)	

Note: \* Incidence proportion is shown per 10^2 treatment starts, including incident exposure at study entry, switches between exposure groups and/or restarts within exposure groups.

Note: \*\* Multiple answers possible.

Note: "Multiple answers possible. Only side effect categories with a proportion > 1% were displayed

Table C-1.3.2	Incidence proportions of treatment discontinuation due to treatment failure, AT population, Starter
Table C-1.3.3	Incidence proportions of treatment discontinuation due to treatment failure, AT population, Switcher
Table C-1.3.4	Incidence proportions of treatment discontinuation due to treatment failure, AT population, Restarter
Table C-1.3.5	Incidence proportions of treatment discontinuation due to treatment failure, AT population, Diagnosis confirmed by surgery
Table C-1.3.6	Incidence proportions of treatment discontinuation due to treatment failure, AT population, Diagnosis based on clinical symptoms
Table C-1.3.7	Incidence proportions of treatment discontinuation due to treatment failure, AT population, Germany
Table C-1.3.8	Incidence proportions of treatment discontinuation due to treatment failure, AT population, Poland
Table C-1.3.9	Incidence proportions of treatment discontinuation due to treatment failure, AT population, Hungary
Table C-1.3.10	Incidence proportions of treatment discontinuation due to treatment failure, AT population, Switzerland

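### The operational definition of treatment failure in SAP 5.4.3 leaves out the exclusion of planned completers stated in SAP 5.2, and no rule covers stops with both kinds of reason

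*SAP*

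**What the plan says.** Treatment failure is one of three primary outcomes and the only one tested for superiority.

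- **SAP 5.4.3** gives the operational definition in two items: "Medication ineffective given as a reason for stopping or switching treatment" and "Side effects of medication given as a reason for stopping or switching treatment". It states no exclusion.
- **SAP 5.2** requires that lack of efficacy, loss of efficacy or an adverse drug reaction caused the stop. It adds that failure "does not include women who stop treatment after pre-defined treatment periods", with six months of a GnRH agonist as the example. The footnote to the objectives in SAP section 2 and protocol section 11 say the same.
- **SAP 5.4.4** places the end of the treatment duration among discontinuations unrelated to failure.
- **The follow-up questionnaire (SAP Appendix II)** offers five reasons for each medication in one list: wish for pregnancy, treatment duration finished, ineffective, side effects, other.
- **Mock Tables C-1.3.1** (failure) and **C-2.1.1** (stops unrelated to failure) each carry the note "Multiple answers possible" on their breakdown of reasons.

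Neither document says how to classify a stop for which both a finished course and a failure reason are given.

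**The concern.** The rule most likely to be programmed is the one in 5.4.3. It stands under the heading for primary outcome definitions and is phrased in the questionnaire's own categories. Applied literally, it makes a woman a failure if she completes a planned course and also ticks side effects or ineffectiveness, although 5.2 excludes her.

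The error would not fall evenly. The OAED comparator consists of GnRH agonists and danazol (SAP 3.2 and 5.1). The protocol introduction says treatment with these drugs has to end after 6 to 12 months, and presents dienogest as a possible long-term option. Planned completions should therefore sit mainly in OAED. Extra failures there move the comparison towards superiority of dienogest.

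**Working it through.** **1. The two definitions side by side**

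| | SAP 5.4.3 | SAP 5.2, SAP section 2 footnote, protocol section 11 |
|---|---|---|
| Link between reason and stop | given as a reason; need not be the only or main one | must have caused the stop |
| Planned completion | not mentioned | excluded |
| Planned completer who also ticks a failure reason | failure, if read literally | not a failure |

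**2. Can one stop carry both kinds of reason?** The note in C-1.3.1 shows that ineffectiveness and side effects can be recorded together. The note in C-2.1.1 shows the same for pregnancy wish, finished duration and other. Both sets come from one five-box list, so ticking across the sets is likely possible. This is an inference: the form's tick instruction is cut off in the extracted text.

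**3. The plan's own figure.** SAP Table 4 assumes failure of 0.30 (reference) and 0.25 (dienogest), one-sided α 0.0167 (z = 2.127), power 90% (z = 1.282) and 2:1 allocation. It states 1,475 and 2,950 women-years. With two proportions and pooled p = (0.30 + 2 × 0.25)/3 = 0.2667:

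n(reference) = [2.127·√(1.5 × 0.2667 × 0.7333) + 1.282·√(0.30 × 0.70 + 0.25 × 0.75/2)]² / 0.05² = (1.1521 + 0.7063)² / 0.0025 ≈ 1,382

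With continuity correction, or with unpooled variance, n is 1,412. These are 4 to 6% below 1,475, so the figure is not reproduced exactly. Power at the stated size is 91.8%, close enough to use that size for illustration. (An event-based calculation on the rate ratio 0.833 gives 1,968 reference women-years and 79.5% power. That is a separate matter and does not affect this point.)

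**4. Size of the shift.** Let c be the share of OAED treatment starts that end at planned completion, and d the share of those where a failure reason is also ticked. The rise in OAED failure is c × d. The documents give neither value, so every c and d below is an assumption.

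To show the effect on a test, assume also:
- true failure is 0.25 in both cohorts;
- no double-ticking occurs under dienogest;
- the comparison is of crude proportions at 1,475 versus 2,950, one-sided α 0.0167.

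The chance of a false superiority finding is then Φ{[(p − 0.25) − 2.127·SE₀]/SE₁}. Here p is the observed OAED proportion, SE₀ the pooled standard error and SE₁ the unpooled one. For p = 0.27: SE₀ = 0.01393, SE₁ = 0.01404, (0.02 − 0.02963)/0.01404 = −0.686, and Φ = 0.246.

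| c | d | Added points | OAED failure reads | False superiority |
|---|---|---|---|---|
| 20% | 2% | 0.4 | 0.254 | 3% |
| 20% | 5% | 1 | 0.26 | 8% |
| 40% | 5% | 2 | 0.27 | 25% |
| 60% | 5% | 3 | 0.28 | 51% |
| 40% | 10% | 4 | 0.29 | 76% |
| 50% | 10% | 5 | 0.30 | 92% |

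To add the full 5 points, d must be 0.05/0.50 = 10% when c is 50%, or 0.05/0.30 = 16.7% when c is 30%.

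**The case against.** The strongest reply is that the plan, read as a whole, already excludes planned completers. The exclusion appears in the protocol, in the SAP objectives footnote and in 5.2. SAP 5.4.4 supports it, and 5.4.3 nowhere withdraws it. This stands in part. A reader might infer that such women are definitely counted as failures, but the documents support only that two definitions are unreconciled and that one of them, taken alone, would count them.

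A reader might also infer from the table notes that one stop can be counted in both tables. The notes do not say so. Each applies to the breakdown inside its own table, and C-2.1.1 is titled as unrelated to failure. Baseline question 11 tells women to tick everything that applies, whereas the corresponding instruction on the follow-up form cannot be read in full.

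The magnitudes are assumed. The hypothesis in 5.2 is stated as an odds ratio, and SAP section 8 (D-3) plans incidence rate ratios and Cox hazard ratios. A shift in crude proportions does not carry over directly to those measures.

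Finally, giving a finished course precedence would drop some genuine failures, such as a woman who stops for an adverse reaction near the planned end and ticks both boxes. That cost is real. The remedy does, however, carry an exclusion the plan already states into the operational rule.

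**Conclusion.** The concern holds as an unresolved conflict in the definition of a primary outcome, and it should be settled before the final analysis. If 5.4.3 is programmed as written, planned completers who also tick a failure reason become failures, contrary to 5.2. The likely direction favours dienogest, because planned courses belong mainly to OAED. Planned completions with double ticks under dienogest would offset part of the shift.

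The number of women affected is unknown. In the illustration, the added OAED failure runs from 0.4 to 5 points, against a planned difference of 5. This rests on assumed completion and double-tick rates, on crude proportions, and on the inference that both kinds of reason can be ticked for one stop. A reader might infer that the expected 0.30 versus 0.25 difference is itself an artefact of classification. The documents do not support that, since they give no completion or double-tick rate.

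**What to change.** Add one sentence to SAP 5.4.3: for the primary analysis, a stop or switch with finished treatment duration among its reasons is not a treatment failure, whatever other reason is given. Report the any-tick classification as a sensitivity analysis. The difference between the two failure counts in each cohort then shows how many stops had mixed reasons.

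The cost is one sentence and one additional run on data already collected. The downside is that some completers with a genuine failure reason are not counted in the primary analysis; the sensitivity analysis shows how much that matters. The choice should be fixed before the final analysis, because choosing between the classifications afterwards could decide the superiority result.

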#### 5.4.4 Definition of secondary outcomes

#### Treatment pattern

Treatment pattern is defined as:

- 1. Treatment discontinuation not related to treatment failure (treatment duration over, trying to become pregnant, other reasons)
- 2. Cohort status/switch of women during follow-up, considering the first treatment switch after baseline

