## II Follow-up questionnaire

	LOGO FIELD ORGANIZAT	ION					ZEG	
				INAS-VIPOS				
			- Follow-	up Questionnaire l	No. [N] –			
					بينال			
If voi	ı have any questions, pleas	e call our fre	ee phone numbe	Count	ry Physician	no. Patient r	no. ID	
_	ometriosis Treatment	o our our m	oc priorio riamo	or. [terepriene namber]				
1.	Have you used any ho	ormonal tr	eatment for y	our endometriosis since	we last heard	from you in [mo	onth/year]?₁	
	☐ Yes → Please fill in a	all medicatio	ns with dates a	nd reasons for stopping / switc	1			e below
Brar	nd name of medication 2	F	rom	То	(Please tick appro		ng	
		month 3	year 4	ongoing 7	☐ Trying to beco☐ Treatment dur☐ Medication ine☐ Side-effects of☐ Which:	ration finished effective f medication		9
		M M L	Y Y Y Y Y year	month year ongoing	Other (e.g. sympto	ome pregnant ration finished effective f medication		10
		M M L	Y 1 Y 1 Y 1 Y 1	W_M   Y_Y_Y_Y   Wear   ongoing	Other (e.g. symptotics) Trying to become treatment dure Medication ine Side-effects of Which: Other (e.g. symptotics)	ome pregnant ration finished effective f medication		
		M_M_L	Y I Y I Y I Y I Y I Y I	month year ongoing	☐ Trying to beco☐ Treatment dur☐ Medication ine☐ Side-effects of Which:	ome pregnant ration finished effective f medication		
					Other (e.g. sympto			
	
 
No, I have not use [month/year] until the provide the medication(s) by
 
	today. e reason fo	r not using the p		☐ Trying to beco ☐ Treatment dur ☐ Medication ine ☐ Side-effects of Which:	ration finished effective f medication		
2.	Since we last heard fro	m vou in	[month/year]	, have you had surgery/la	Other (e.g. sympto		ndometrics	
	□ No → Go to ques If yes, please specify to	tion 3 he type an	☐ Yes Id date of surg	ery (if known) in the table lery, diagnostic laparoscop	below (i.e. excis	ion of lesions, re	emoval of ova	
	Operation 12					Date		
						M_M_13_Y_Y month 13 y	year 14	
						M_M Y_Y	year	
Medi 3.	cal History  We last heard from yo	u in [mon	th/year]. Sind	ce then, have you had an	v of the followi	ng diseases?		
Ane	emia 15	□ No	☐ Yes, dia		Y Y Y Y Y 17			
7			I was	treated by a physician 66 treated with iron tablets 18	year 17	□ Yes	□ No	
				treated with an iron infusion	Lan	□ Yes	□ No □ No	
				treated with a blood transfus		□ Yes	□ No	
				r treatment?. 21		□ Yes	□ No	
			If yes	, which?				_ 22
	p venous thrombosis	□ No	☐ Yes, in	month 24	year 25			

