#### Section C-2 Secondary outcomes

Section C-2.1 Incidence proportions of treatment discontinuation unrelated to treatment failure

Table C-2.1.1 Incidence proportions of treatment discontinuation unrelated to treatment failure, AT population, Complete cohort

	DNG		OAED			NAED		Allocation unknown	Total
		GnRH-a	Danazol	All OAED	СНС	Other progestin	All NAED		
Number of treatment starts	xx	xx	xx	xx	xx	xx	xx	xx	xx
Treatment									
discontinuation	XX	XX	XX	XX	XX	xx	xx	xx	xx
IP* (95% CI)	xx.x (xx.x-x.x)	xx.x (xx.x-x.x)	xx.x (xx.x–x.x)	xx.x (xx.x-x.x)	xx.x (xx.x-x.x)	xx.x (xx.x-x.x)	xx.x (xx.x–x.x)	xx.x (xx.x–x.x)	xx.x (xx.x-x.x)
Thereof**									
Trying to become	XX	xx	xx	XX	xx	xx	XX	xx	xx
pregnant	xx.x (xx.x-x.x)	xx.x (xx.x-x.x)	xx.x (xx.x-x.x)	xx.x (xx.x-x.x)	xx.x (xx.x–x.x)	xx.x (xx.x-x.x)	xx.x (xx.x-x.x)	xx.x (xx.x-x.x)	xx.x (xx.x-x.x)
Treatment duration	xx	xx	xx	XX	xx	xx	XX	xx	xx
finished	xx.x (xx.x-x.x)	xx.x (xx.x-x.x)	xx.x (xx.x-x.x)	xx.x (xx.x-x.x)	xx.x (xx.x–x.x)	xx.x (xx.x-x.x)	xx.x (xx.x-x.x)	xx.x (xx.x-x.x)	xx.x (xx.x-x.x)
Other	xx	xx	xx	xx	xx	xx	xx	xx	xx
	xx.x (xx.x-x.x)	xx.x (xx.x-x.x)	xx.x (xx.x-x.x)	xx.x (xx.x-x.x)					
Thereof**									
Physician's advice	xx	xx	xx	xx	XX	xx	xx	xx	xx
	xx.x (xx.x-x.x)	xx.x (xx.x-x.x)	xx.x (xx.x-x.x)	xx.x (xx.x-x.x)					
< <category>></category>	xx	xx	xx	xx	XX	xx	xx	xx	xx
	xx.x (xx.x–x.x)	xx.x (xx.x-x.x)	xx.x (xx.x-x.x)	xx.x (xx.x-x.x)	xx.x (xx.x–x.x)	xx.x (xx.x-x.x)	xx.x (xx.x-x.x)	xx.x (xx.x-x.x)	xx.x (xx.x-x.x)

Note: 'Incidence proportion is shown per 102 treatment starts, including incident exposure at study entry, switches between exposure groups and/or restarts within exposure groups.

Note: \*\*Multiple answers possible.

Table C-2.1.2	Incidence proportions of treatment discontinuation unrelated to treatment failure, AT population, Starter
Table C-2.1.3	Incidence proportions of treatment discontinuation unrelated to treatment failure, AT population, Switcher
Table C-2.1.4	Incidence proportions of treatment discontinuation unrelated to treatment failure, AT population, Restarter
Table C-2.1.5	Incidence proportions of treatment discontinuation unrelated to treatment failure, AT population, Diagnosis confirmed by surgery
Table C-2.1.6	Incidence proportions of treatment discontinuation unrelated to treatment failure, AT population, Diagnosis based on clinical symptoms
Table C-2.1.7	Incidence proportions of treatment discontinuation unrelated to treatment failure, AT population, Germany

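### Every stop for 'other reasons', including physician's advice, is classed as unrelated to treatment failure, although the plan defines this primary outcome by the cause of stopping

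*SAP*

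**What the plan says.** **Definition by cause.** SAP 5.2 defines treatment failure as "cessation of treatment caused by lack of efficacy, loss of efficacy or an adverse drug reaction", leaving out planned ends of treatment. Protocol section 11 and the footnote to SAP section 2 say the same.

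**Definition by reason given.** SAP 5.4.3 has two criteria: "Medication ineffective given as a reason for stopping or switching treatment" and "Side effects of medication given as a reason for stopping or switching treatment".

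**The residual class.** SAP 5.4.4, under Treatment pattern, has a secondary outcome described as "Treatment discontinuation not related to treatment failure (treatment duration over, trying to become pregnant, other reasons". It makes no exception for 'other reasons'.

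**The table.** Mock Table C-2.1.1 is titled "Incidence proportions of treatment discontinuation unrelated to treatment failure, AT population, Complete cohort". It has an 'Other' row, and "Physician's advice" is a sub-row of it.

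**The source.** The woman ticks a reason on the follow-up questionnaire (SAP Appendix II, question 1). The legible choices are trying to become pregnant, treatment duration finished, ineffective, side effects (with a space to say which), and a box that survives in the extracted text as "Other (e.g. sympto". No legible choice names the physician. The note to Table C-1.3.1 says "Multiple answers possible".

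**The concern.** The two definitions part company on a stop that was caused by inefficacy or an adverse reaction but entered only under 'Other'. SAP 5.2 makes it a failure; SAP 5.4.3 and 5.4.4 make it a non-failure. Physician's advice shows the difficulty well, because it tells us who prompted the stop and not why. Neither document gives a rule for reading the 'Other' text and moving such a stop to its cause.

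Treatment failure is the only primary outcome tested for superiority, and it is sized on 25 against 30 failures per 100, so a few misfiled stops per 100 matter. The protocol (sections 3, 8 and Appendix 2) gives anemia and depression physician contact and blinded adjudication because lay reports are often misclassified. It states no such check on the reason for stopping, and the SAP plans no sensitivity analysis on how that reason is coded.

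**Working it through.** **1. Follow one stop through the text.** A physician advises a woman to stop because of an adverse reaction, and she ticks 'Other' alone.
- SAP 5.2: an adverse drug reaction caused the cessation, so it is a failure.
- SAP 5.4.3: neither criterion was given as a reason, so it is not a failure.
- SAP 5.4.4 and Table C-2.1.1: placed among stops unrelated to failure.

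If she also ticks side effects, SAP 5.4.3 is met and nothing is lost. The problem is confined to stops recorded solely as 'Other'.

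**2. Reproduce Table 4.** Inputs from SAP section 4: failure 0.30 (reference) and 0.25 (DNG), one-sided α 0.0167, power 90%, DNG to reference 2:1, giving 1,475 and 2,950 women-years. With the variance taken at 0.30 in both cohorts:

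n(ref) = (z₁₋α + z₁₋β)² × 0.30 × 0.70 × (1 + 1/2) / 0.05² = (2.127 + 1.282)² × 0.315 / 0.0025 = 1,465

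so n(DNG) = 2,930. Both are within 1% of the stated figures, and the stated total follows: 2,950/0.10 = 1,475/0.05 = 29,500.

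**3. Effect of losing failures to 'Other'.** The share lost is an assumption, because the documents give none. Let m be the share of true failures recorded only as 'Other', so that each observed rate is p = true rate × (1 − m). With n₁ = 1,475 (reference) and n₂ = 2,950 (DNG):

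P(superiority) = Φ[(p₁ − p₂ − 2.127 × SE₀) / SE₁]

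where SE₀ uses the pooled rate and SE₁ the separate rates. With no loss, p₁ − p₂ = 0.05, SE₀ = 0.01410 and SE₁ = 0.01435, so the power is Φ(1.394) = 91.8%, against the planned 90%.

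| True ref / DNG | Lost in ref | Lost in DNG | Observed ref / DNG | P(superiority) |
|---|---|---|---|---|
| 0.30 / 0.25 | 0% | 0% | 0.300 / 0.250 | 91.8% |
| 0.30 / 0.25 | 10% | 10% | 0.270 / 0.225 | 87.6% |
| 0.30 / 0.25 | 20% | 20% | 0.240 / 0.200 | 82.0% |
| 0.30 / 0.25 | 30% | 30% | 0.210 / 0.175 | 75.0% |
| 0.30 / 0.25 | 10% | 0% | 0.270 / 0.250 | 24.6% |
| 0.30 / 0.30 | 10% | 10% | 0.270 / 0.270 | 1.67% |
| 0.30 / 0.30 | 0% | 5% | 0.300 / 0.285 | 13.9% |
| 0.30 / 0.30 | 0% | 10% | 0.300 / 0.270 | 48.7% |
| 0.30 / 0.30 | 10% | 20% | 0.270 / 0.240 | 51.8% |

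Where the true rates are 0.30 and 0.25, the last column is power. Where both are 0.30, it is the chance of a false superiority finding. Equal loss costs power but does not raise type I error. Unequal loss distorts the result in whichever direction the imbalance runs.

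This two-proportion calculation treats the Table 4 women-years as counts of women. It stands in for the planned odds ratio (SAP 5.2) and Cox model (SAP section 8, D-3).

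**The case against.** **Few stops may be affected.** The questionnaire offers ineffective and side effects as direct choices and more than one answer is possible, so only stops recorded solely as 'Other' are lost. This stands. A reader might infer that all failures recognised by the doctor drop out of the endpoint; the documents do not support that. Nor is every physician-advised stop a failure, and the documents do not say why the advice was given.

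**Coding and disclosure may already help.** SAP 6.1 sends information not otherwise coded to a coding dictionary that is not reproduced, the printed example for the 'Other' box is cut off in the extracted text, and Table C-2.1.1 shows physician-advised stops by cohort with confidence intervals. This too stands in part: an imbalance would be visible. It would not be corrected, because SAP 5.4.4 still places the whole class outside failure and no sensitivity run is planned.

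**The tempting stronger reading is that the rule favours DNG.** On this argument, physician-advised stops of time-limited GnRH-agonist or danazol courses are mostly planned ends, whereas those of open-ended DNG use have a clinical trigger. The documents do not support it. Planned ends have their own box, and in any case they hide no failures. The protocol introduction describes androgenization with danazol and bone loss with GnRH agonists; a stop for either, recorded only as 'Other', would hide a reference-cohort failure and work against DNG. One can choose a loss of 5 per 100 in DNG and none in the reference cohort, which turns equal rates of 0.30 into exactly the design contrast of 0.25 against 0.30. That assumes one in six DNG failures is hidden and no reference failure is, and nothing in the documents points to it.

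**Conclusion.** The concern holds as a contradiction within the plan about a primary outcome. SAP 5.2 and Protocol section 11 define failure by cause; SAP 5.4.3 and 5.4.4 classify by the reason given and put every 'other' reason outside failure. Stops caused by inefficacy or an adverse reaction but recorded only as 'Other' are therefore misclassified in the superiority comparison.

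The share affected and its direction by cohort are unknown, so the plan cannot be said to favour either cohort. The figures above show only how sensitive the test is: assumed losses of 5% to 30% of failures move it from a modest loss of power, if equal, to about 49% false superiority or about 25% power, if 10% is lost on one side only. They rest on the Table 4 rates and sizes and on assumed losses. The point should be settled before the final analysis, since the remedy is cheap and protects the superiority conclusion.

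**What to change.** - **SAP 5.4.3 and 5.4.4:** state that stops recorded as 'other' or as physician's advice are coded to their underlying cause from the reason text already collected, by coders blinded to cohort. They count as treatment failure when the stated cause is inefficacy or an adverse reaction.
- **Table C-2.1.1:** show stops with no stated cause as 'cause unknown', not as unrelated to treatment failure. Keep the count of physician-advised stops visible by cohort, because it lets a reader see any imbalance.
- **Sensitivity analysis:** repeat the treatment-failure model with the cause-unknown and physician-advised stops counted as failures.
- **Do not infer cause from coincidence:** an anemia, depression or SAE report from the same period should not be used to assign the cause. That would tie this primary outcome to the other two and turn coincident events into failures.

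Cost: SAP wording, blinded recoding of text already held, and one extra model run. Some causes will stay unknown, and the stated failure proportions may rise.
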